2.1 OBJECTIVES AND SCIENTIFIC AIMS

Primary Objective:

- Determine whether there is a reduction in the percentage of pediatric neuroblastoma patients undergoing a bone marrow procedure who require post-procedural opioid analgesia within 24 hours (+/- 4 hours) of the procedure with the addition of local ropivacaine.

Secondary Objective:

Determine whether there is a difference in:

- 24 hours (+/- 4 hours) post-procedure opioid consumption in morphine equivalents (mg/kg/day)
- Percentage of patients requiring non-opioid analgesia within 24 hours (+/- 4 hours) of procedure
- Standardized pain scores (Wong-Baker FACES® Scale)
- Time to first opioid medication
- Short-term quality of life
- Adverse outcomes with the addition of local ropivacaine

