3.3 Rationale

The purpose of this study is to investigate whether subcutaneous and periosteal infiltration of a local anesthetic agent, ropivacaine, will reduce the percentage of patients requiring post-procedural opioid analgesia and improve quality of life in the day following the procedure. A similar study recently demonstrated that topical analgesia for lumbar punctures reduced the amount of propofol used in pediatric oncology patients.⁹ However, no study has been done to investigate the efficacy of local analgesia in combination with propofol for bone marrow procedures. For this reason, a trial evaluating the effect of the addition of local analgesia is both justified and necessary. Local analgesia acts to limit the initiation of nociceptive pathways prior to the traumatic insult, in this case, subcutaneous and periosteal infiltration by a bone marrow aspiration or biopsy needle. Ropivacaine is an example of a local anesthetic agent that blocks both the initiation and conduction of nerve impulses by decreasing the neuronal membrane's permeability to sodium ions.¹⁰ It is an amino-amide local anesthetic that is a pure S-(-)-enantiomer with lower lipid solubility than racemic mixtures; these features allow ropivacaine to have a higher safety profile with less cardiovascular and central nervous system toxicity than racemic lidocaine and bupivacaine.¹⁰ Its onset of action is listed as "fast" with infiltration. i.e. within 3 to 15 minutes.¹¹ Its duration of action is 3 to 15 hours.¹¹ Therefore, due to its effect on nociceptive pathways, rapid onset and moderate duration of action while maintaining a low toxicity profile, ropivacaine is a reasonable option for local analgesia for bone marrow procedures. This is the first time ropivacaine will be directly injected into the bone marrow site at MSKCC Pediatrics.

Primary and secondary outcome measures were carefully selected after reviewing pediatric pain literature. Within pain clinical trials, analgesic efficacy can be measured by the ability to reduce or eliminate the need for rescue analgesia. "Rescue analgesia-sparing" has been identified as practical and feasible surrogate primary endpoint^{12,13}. A systematic review of

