12.0 CRITERIA FOR THERAPEUTIC RESPONSE/OUTCOME ASSESSMENT

12.1 To assess primary objective, we will determine and compare for each study intervention the percentage of patients who required opioid analgesia between the time of bone marrow procedure and 24 hours (+/- 4 hours) after the procedure.

12.2 For the secondary objectives:

- a) We will determine and compare for each study intervention the percentage of patients who used any non-opioid analgesia within 24 hours (+/- 4 hours) after bone marrow procedure.
- b) We will calculate and compare for each study intervention the total dose of opioid consumption within 24 hours (+/- 4 hours) of the bone marrow procedure using mg/kg/day morphine equivalent.

Drug	IV conversion factor	PO conversion factor
Morphine	10mg	30mg
Fentanyl	0.250mg (250mcg)	—
Hydromorphone	2mg	8mg
Oxycodone	—	20mg
Oxymorphone	1mg	10mg
Codeine	75mg	130mg
Methadone	1mg	2mg
Hydrocodone	—	30mg

c) We will also determine the time to the first opioid administration. The starting point for this time will be the time of transfer to the PRR which will be documented by the PRR RN. This time will be recorded on the parent worksheet by the PRR RN.

d) We will assess standardized pain scores at 3 time points: (1) the maximum recorded pain score in the PRR, (2) at 6 hours (+/- 1 hour) and (3) 24 hours (+/- 4 hours) after the bone marrow procedure. Pain scores 2 and 3 will be recorded by the parent after discharge from MSKCC. We will use the following validated pain scales: Wong-Baker FACES® Pain Rating Scale for patients between 3-18 years of age for patient-reported pain when asked by post-anesthesia recovery room nurses upon emergence from anesthesia and by inpatient nurses or family members in the outpatient setting upon discharge from the post-anesthesia recovery unit. We will compare pain scores between study interventions.

e) The QOL metric is a brief instrument that will assess post-procedural quality of life within 24 hours (+/- 4 hours) of the bone marrow procedure. This instrument assesses the following domains: sleep, physical functioning, emotional functioning and social functioning. This brief measurement tool will be adapted from a validated metric for pain interference in pediatric patients: NIH PROMIS® Parent Proxy Item Bank v1.0 – Pain Interference, which is a 13-item questionnaire. However, given that our study has rapid, frequent assessments, we will use an

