14.0 BIOSTATISTICS

This is a randomized two arm cross-over study investigating the effectiveness of the addition of ropivacaine to the standard of care on pain among pediatric neuroblastoma patients undergoing repeated procedures. The two drug combinations are standard of care (Intervention A) or standard of care plus ropivacaine (Intervention B, see Section 4.1). Patients will be randomized to either Arm 1 (AB sequence) or Arm 2 (BA sequence, see Figure in Section 1) to determine whether standard of care or standard of care plus ropivacaine will be administered in the first of two procedures. Patients will cross over during the second procedure. Sample size calculation is based on the primary outcome: the proportion of patients requiring post-procedural opioid analgesia ("rescue opioids") within 24 hours (+/- 4 hours) post procedure. A needs assessment conducted in pediatric patients at MSKCC suggests that this proportion is about 30% under Intervention A (standard of care). We plan to enroll 50 patients (total of 100 procedures).

This is a crossover study in which we assume that there will be no period effect (i.e., if patient's response in the subsequent procedure is affected by the drug from the first procedure). Due to the estimated two month interval between the two procedures and the duration of action of less than 15 hours for either drug combinations, we can assume no period effect. The primary outcome (whether the patient received rescue opioids) will be evaluated with GEE (generalized estimating equations) for binary data with logit link function clustered by patients²³. The model

will include the drug indicator, procedure order, and an exchangeable correlation structure to address the correlation between multiple observations from the same patient. GEE has the advantage of being able to include data from only one of a patient's two procedures, in order to accommodate the (rare) case in which the patient drops out / withdraws prior to the second procedure. With complete data, however, this approach simplifies to a McNemar's test. The power and sample size calculations will be based on McNemar's test.

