Secondary outcome of standardized cumulative opioid consumption within 24 hours (+/- 4 hours) (morphine equivalents, mg/kg/day) will be summarized and compared between the two drugs using linear GEE models with the same factors as described above, including of the other potential factors identified from the analysis of the primary outcome. Additionally, time to first opioid use within the first 24 hours (+/- 4 hours) post procedure will be estimated using the Kaplan-Meier method and compared between the two drugs using the clustered logrank test. This is appropriate as patients may never require any opioids and will hence be censored at 24-hours. The proportion of patients requiring non-opioid analgesia within 24 hours (+/- 4 hours) of procedure will be compared between the two drugs using GEE (for binary data) as described for the primary outcome.

Post-operative pain reported on the Wong-Baker FACES® Pain Rating Scale (converted to scale of 0-10) will be measured at 3 time points: in the PRR, at 6 hours (+/- 1 hour) and 24 hours (+/- 4 hours) after the procedure. If more than one pain score is recorded during the PRR,

then the maximum pain score during the PRR will be included in analyses. Pain scores will be compared between the two drugs using a linear GEE model with drug indicator, procedure order and the exchangeable correlation structure for the 3 time points. The GEE models appropriately account for correlation among within-individual repeated measures, sequence of drugs, and allow for missingness (i.e., if the respondent does not provide complete follow-up data). Short-term QOL and activity level will be reported based on the (NIH PROMIS® Parent Proxy Item Bank v1.0 – Pain Interference) as individual items. QOL measures will only be recorded once at 24-hours post-procedure. We will use a linear GEE model to analyze the differences in QOL item-measures between the two drugs. Drug indicator and procedure order will be included as covariates. Overall rate of any complications or major adverse events and the rates of specific adverse outcomes related to the addition of local ropivacaine will also be compared between drugs using GEE (for binary data). These analyses are exploratory because they are of secondary interest and we do not have prior data to estimate statistical power.

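### The pain-score model has no time or drug-by-time term, so it gives one drug effect averaged over three time points, the last of them after ropivacaine's stated duration of action

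*Combined protocol and SAP*

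**What the plan says.** Section 12.0, item d, sets out the outcome: "We will assess standardized pain scores at 3 time points". Section 14.0 repeats that pain "will be measured at 3 time points: in the PRR, at 6 hours (+/- 1 hour) and 24 hours (+/- 4 hours) after the procedure". When several recovery-room (PRR) readings exist, "the maximum pain score during the PRR will be included in analyses". The two later scores are single values recorded by the parent after discharge.

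The analysis in Section 14.0 is a "linear GEE model with drug indicator, procedure order and the exchangeable correlation structure for the 3 time points". The further covariates that Section 14.0 allows in the GEE models are the number of biopsies and aspirations and the ropivacaine dose. Time is not among them, and no comparison at a named time point is planned.

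On how long the drug acts, Section 3.3 says of ropivacaine: "Its duration of action is 3 to 15 hours". Section 14.0, arguing against carry-over between procedures, relies on "the duration of action of less than 15 hours for either drug combinations".

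The pain-score objective in Section 2.1 names no time point. Section 14.0 describes the secondary analyses as exploratory, with no prior data from which to estimate power.

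**The concern.** A single drug coefficient describes the data well only if the drug effect is about the same at all three times. The plan's own figures give reason to doubt that. The 24-hour window runs from 20 to 28 hours, entirely beyond the stated duration of action. The 6-hour window (5 to 7 hours) lies inside it at the 15-hour end and outside it at the 3-hour end.

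Two things are at stake. First, the model cannot say when the drug helps, although pain is deliberately measured at three times and Section 3.3 introduces pain-score differences over time or with an intervention as a secondary outcome. If the effect fades, the reported figure is smaller than the effect at its peak, and a reader cannot tell a small lasting effect from a larger brief one.

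Second, mean pain is likely to differ across the three scores, not least because the first is a maximum and the others are single readings. With no time term, any imbalance between interventions in which scores are missing passes into the drug coefficient. Section 14.0 relies on GEE to cope with incomplete follow-up.

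**Working it through.** **The plan's own figure.** The documents give no effect size, SD, correlation or power for pain scores. The only power figure belongs to the primary outcome. With rates of 30% and 10% and correlation 0.4, the joint probability is 0.3 × 0.1 + 0.4 × √(0.3 × 0.7 × 0.1 × 0.9) = 0.085. The discordant cells are therefore 0.215 and 0.015, and exact two-sided McNemar power at 45 pairs is 80.9%. The stated 80% reproduces, and nothing below affects it.

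**What the coefficient estimates.** With complete, balanced data and an exchangeable correlation, the drug coefficient is the plain mean of the three time-specific effects, (d_PRR + d_6h + d_24h)/3. As a share of the PRR effect:
- full, full, zero: 2/3 = 67%
- full, half, zero: 1.5/3 = 50%
- full, zero, zero: 1/3 = 33%
- full, full, full: 100%

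Simulated GEE fits agree (45 patients, two procedures, three times, 300 runs per pattern, assumed full effect −1.5 points):

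| Effect pattern | Pooled coefficient | PRR effect, drug-by-time model |
|---|---|---|
| full, full, zero | −0.97 | −1.47 |
| full, half, zero | −0.75 | −1.49 |
| full, full, full | −1.50 | −1.48 |

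**Precision and power.** Assumptions: 45 complete pairs, SD 2.5, correlation 0.5 between scores within a procedure, 0.4 across procedures at the same time and 0.3 across procedures at different times.
- Variance of the drug difference at one time: 2 × (1 − 0.4) × 6.25 = 7.5.
- Covariance between differences at two times: 2 × (0.5 − 0.3) × 6.25 = 2.5.
- SE, PRR alone: √(7.5/45) = 0.408.
- SE, mean of PRR and 6 h: √[((2 × 7.5 + 2 × 2.5)/4)/45] = √(5/45) = 0.333.
- SE, all three pooled: √[((3 × 7.5 + 6 × 2.5)/9)/45] = √(4.167/45) = 0.304.

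Power = Φ(effect/SE − 1.96):

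| True effects (PRR, 6 h, 24 h) | Pooled effect | Power, pooled | Power, PRR and 6 h mean | Power, PRR alone |
|---|---|---|---|---|
| 1, 1, 1 | 1.00 | 91% | 85% | 69% |
| 1, 1, 0.5 | 0.83 | 78% | 85% | 69% |
| 1, 1, 0 | 0.67 | 59% | 85% | 69% |
| 1, 0.5, 0 | 0.50 | 38% | 61% | 69% |
| 1, 0, 0 | 0.33 | 19% | 32% | 69% |

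With 1 point at PRR and 6 h, pooled and early-average power are equal when the 24-hour effect is 3 × (3 × 0.304) − 2 ≈ 0.74 point. For the 1, 1, 0 pattern at SD 2.5, letting the correlation between the time-specific differences run from 0.2 to 0.8 moves pooled power from 67% down to 42%, and early-average power from 89% down to 73%. No contrast is best under every pattern.

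**Time main effect, complete data.** Each patient contributes every time point under each intervention, so time is balanced against drug. In the full, full, zero simulation the estimate (−0.973), SE (0.305) and power (0.897) were identical with and without a time main effect.

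**Time main effect, unequal missingness.** Assume no drug effect, means 4, 2.5 and 1, and 24-hour scores missing in 30% of procedures under one intervention and 10% under the other.
- 30% missing: (4 + 2.5 + 0.7 × 1)/2.7 = 2.667.
- 10% missing: (4 + 2.5 + 0.9 × 1)/2.9 = 2.552.
- False difference: 0.11 point.

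Simulated GEE fits under the same assumptions gave 0.12 to 0.13 without a time term and 0.00 to 0.01 with it.

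**The case against.** The strongest reply is that an average over the first day is a legitimate target. A reader might infer that the trial wants the early effect and that the 24-hour score contaminates it, but the documents do not say so. The pain objective singles out no time point. Section 3.3 asks whether ropivacaine "will reduce the percentage of patients requiring post-procedural opioid analgesia and improve quality of life in the day following the procedure". The opioid and non-opioid endpoints run to 24 hours (+/- 4 hours), and the needs assessment in Section 3.2 cites persistent pain the next day in 12 of 26 patients. This stands.

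A nil effect at 24 hours is also an inference. Duration of action is not duration of benefit, and Section 3.3 explains the rationale as limiting the initiation of nociceptive pathways, which leaves room for later benefit. This stands too: dilution and loss of power are conditional, and a persistent effect reverses the power comparison (91% pooled against 85%).

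Different means at the three times, including the maximum against single readings, do not by themselves bias the drug effect. Bias needs missingness that differs by intervention. Parents are blinded and families are telephoned. Section 13.0(a) takes patients off study for analgesic use outside the algorithm, which could fall unevenly, but the documents do not say that it will. The 30% and 10% are therefore illustrative, and the resulting 0.11 point is only about 0.4 of the pooled SE (0.11/0.304).

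None of this answers the core point. If next-day pain matters, a separate 24-hour estimate serves that aim better than an average that hides it.

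**Conclusion.** The point holds in limited form. The model as written yields one averaged drug effect, cannot show when the drug helps, and leaves undefined which pain effect the trial intends to estimate. If the 24-hour effect is nil, the coefficient is about 33% to 67% of the recovery-room effect; if the effect persists, there is no dilution and pooling is the more powerful choice. Omitting the time main effect matters only when missingness differs by intervention, with a false difference of about 0.11 to 0.13 point under the assumed rates and means. All pain-score effects, SDs, correlations and missingness rates here are assumptions.

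Two stronger readings are not supported: that the plan necessarily understates the benefit, and that the mean of the recovery-room and 6-hour scores ought to be the main contrast. The second is a preference. By the 3-hour end of the stated duration the 6-hour score may also fall outside the drug's action, and under effects of 1, 0, 0 that average has 32% power against 69% for the recovery room alone.

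This is a minor improvement to an exploratory secondary outcome. The primary analysis and the sample size are untouched.

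**What to change.** In Section 14.0, add time (recovery room, 6 h, 24 h) as a categorical factor and the drug-by-time interaction to the pain-score GEE. Report the drug difference with its confidence interval at each of the three times. Have the sponsor state in advance which contrast or average is the main one; an average over all three is acceptable if it is declared as the target.

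The cost is a sentence or two of text and no new data. The model gains two sets of terms (two coefficients for time, two for drug-by-time). Each time-specific estimate is less precise than the pooled one: under the assumptions above, an SE of 0.408 against 0.304, so intervals about a third wider (0.408/0.304 = 1.34). Three differences in place of one also mean three comparisons, which is why the main one should be named beforehand.

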4.3 Intervention

Intervention A: The standard of care agent will be administered intravenously by an anesthesiologist as per current institutional practice. An empty decoy syringe will be provided by the pharmacy and taken to the procedure room by appropriate staff as sometimes parents accompany their children into the procedure room prior to anesthesia administration. The empty syringe will be clearly marked and discarded.

Intervention B: The standard of care agent will be administered intravenously by an anesthesiologist as per current institutional practice. Once the anesthetic effect is achieved as determined by the anesthesiologist, the proceduralist physician will inject subcutaneous and periosteal ropivacaine prior to bone marrow aspiration and biopsy at each site (bilateral anterior and posterior iliac crests). Ropivacaine will be provided by the MSKCC PDH Pharmacy and will

be administered at standard dosing of 2mg/kg of a 0.5% solution (5mg/ml) and delivered to the procedure room by appropriate staff.

The following process occurs after every procedure. Patients will complete the procedure and recover in the PRR for an approximate time of 30 to 90 minutes. In the PRR, trained RNs who are blinded to the study combination will assess patient pain based on a validated self-report pain scale and administer pain medication when necessary based on a standard pain management algorithm (Appendix 2.2). After recovery in the PRR, patients will be discharge home. Parents/parents will assess their child's pain on a validated self-report pain scale and administer pain medication when necessary based on a standard pain management algorithm (Appendix 2.2).

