11.0 TOXICITIES/SIDE EFFECTS

11.1 DEFINITION OF TOXICITIES:

- Common - Happens to 20-100 patients out of every 100
- Occasional - Happens to 4-20 patients out of every 100
- Rare - Happens to 3 or fewer patients out of every 100

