11.2 LOCAL INFILTRATION OF ROPIVACAINE^{11, 25-28}

Common	Occasional	Rare
None	None	
• Allergic reaction with any route of administration• Arrhythmia with intravascular administration*• Seizure with intravascular administration* 
*Reported with inadvertent intravascular administration

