Institutional monitoring plan for phase I and phase II trials: Memorial Sloan-Kettering Cancer Center (MSKCC) has established standard procedures for data safety monitoring of clinical research. For Phase II trials, these procedures include consideration of accrual rates, toxicity, adherence to dose-escalation schedules, adverse event notification and data recording. Therapeutic responses are logged on a central database and approximately 50% are reviewed by an independent committee. An annual report of the trial's progress is sent to the IRB. All of the procedures for Phase II studies outlined in MSKCC's policy are applicable to the current trial and will be followed by the investigators. The analysis of safety will include all patients who receive at least one dose of study medication. Adverse events, including all toxic effects of treatment, will be tabulated individually, and summarized by body system, according to study medication, and according to severity or toxicity grade. Laboratory data will be tabulated and summarized by descriptive statistics, as well as on the basis of MSKCC specified normal range.

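### The planned binary GEE for specific ropivacaine-related adverse outcomes has no finite answer when one intervention has no events, which is certain or likely depending on an event definition the plan leaves open

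*Combined protocol and SAP*

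**What the plan says.** Section 2.1 lists adverse outcomes with added ropivacaine among the secondary objectives. Section 14.0 gives the method. After an overall complication rate, it turns to individual events: "rates of specific adverse outcomes related to the addition of local ropivacaine will also be compared between drugs using GEE". The adverse-event sentence specifies only GEE for binary data. The one binary GEE that Section 14.0 sets out in full is for the primary outcome, a "GEE (generalized estimating equations) for binary data with logit link function clustered by patients", and that model "will include the drug indicator, procedure order, and an exchangeable correlation structure". No rule is given for zero or very sparse counts. Section 14.0 calls the secondary analyses exploratory and claims no power for them.

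On exposure, Section 4.3 gives no ropivacaine under Intervention A: "An empty decoy syringe will be provided by the pharmacy". On expected frequency, Section 11.2 leaves the common and occasional columns empty and lists three rare events: "Allergic reaction with any route of administration", and arrhythmia and seizure with intravascular administration. Section 11.1 defines the category as "Rare - Happens to 3 or fewer patients out of every 100".

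Section 16.2 separately says "The analysis of safety will include all patients who receive at least one dose of study medication", and plans tabulation of adverse events by study medication, body system and grade.

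**The concern.** A logit model estimates a log odds ratio, which is finite only if both interventions have at least one event and at least one non-event. The plan applies such a model to outcomes that are either absent under A by definition or rare enough for an empty cell to be a likely result. It does not say which definition applies, and it names no alternative method.

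The failure need not announce itself. GEE software can stop, report convergence and print a coefficient, standard error and p-value that reflect the stopping rule and not the data. A single event could then be reported as overwhelming evidence of harm, or a table without events as a fitted null result. Section 3.3 says this is the first direct injection of ropivacaine into the bone marrow site in this department, so the safety result should be reported in a form that can be trusted.

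**Working it through.** **Inputs.** "We plan to enroll 50 patients (total of 100 procedures"), so 50 procedures under each intervention (Section 14.0). No ropivacaine under A (Section 4.3). At most 3 in 100 patients for each listed rare event (Section 11); each patient has one B procedure, so this is at most 3% of B procedures per event type.

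**The plan's own figures.** None is given for adverse events. The figures behind the 50 patients do reproduce. With rates of 30% and 10% and correlation 0.4, the probability of an event at both procedures is 0.30 × 0.10 + 0.4 × √(0.30 × 0.70 × 0.10 × 0.90) = 0.085, leaving discordant probabilities 0.215 and 0.015. Exact two-sided McNemar power at 45 patients is 80.9%, against 80% stated, and 45 / (1 − 0.10) = 50.

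**Reading 1: outcomes defined by relatedness.** The A count is 0 of 50 by construction. With x events under B, the odds ratio is [x / (50 − x)] / [0 / 50]: infinite if x ≥ 1 and undefined if x = 0. This does not depend on sample size or on the B rate. At the 3% ceiling, the expected number of B events of a given type is 50 × 0.03 = 1.5, with probability 0.97^50 = 0.218 of none.

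**Reading 2: events counted by type, whatever the cause.** The documents give no rate under A. Assume the same rate p under both interventions, independent between procedures. The probability of no events in one intervention is z = (1 − p)^50, and the probability that at least one intervention has none is 1 − (1 − z)².

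| p | z | At least one intervention with no events |
|---|---|---|
| 1% | 0.605 | 84% |
| 2% | 0.364 | 60% |
| 3% | 0.218 | 39% |

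Keeping B at 3% and letting A range from 0.5% to 3%, the last column runs from 83% down to 39%.

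**What the model prints.** A logit GEE with drug and order terms, exchangeable correlation and robust standard errors was fitted to 50-patient crossover data with no events under A. All of these fits were reported as converged.

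| Events A : B | Coefficient | Robust SE | Model p | Exact McNemar p |
|---|---|---|---|---|
| 0 : 1 | 22.5 | 1.02 | about 1e-107 | 1.0 |
| 0 : 2 | 23.2 | 0.74 | about 1e-218 | 0.50 |
| 0 : 3 | 23.8 | 122 | 0.85 | 0.25 |
| 0 : 4 | 24.1 | 524 | 0.96 | 0.125 |

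The results also change with which patients have the events. With 0 : 2, the p-value is about 1e-218 in some allocations and above 0.9 in others. With 0 : 0 the model reports a coefficient near 0 and p near 1. With events on both sides it behaves: 1 : 3 gave coefficient 1.14, SE 1.19, p = 0.34.

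**What exact methods give.** For 0 of 50, the Clopper-Pearson 95% upper limit is 1 − 0.025^(1/50) = 7.1%; for 0 of 45 it is 7.9%. Exact McNemar needs a split of 6 : 0 for two-sided p < 0.05 (2 × 0.5^6 = 0.031; 5 : 0 gives 0.0625). The chance of six or more events among 50 B procedures at 3% is 0.4%.

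**The case against.** The strongest reply is that the plan already reports safety descriptively. Section 16.2 tabulates adverse events by study medication and grade, so counts will exist whatever the GEE does. That stands: a reader might infer that safety would go unreported, and the documents do not support this. The defect lies in the between-drug contrast and in the lack of exact intervals.

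Second, a reader might infer that these events cannot occur under A, so the comparison fails in every case. That is only one reading. A comparison between drugs makes most sense for event types counted under both interventions, and allergic reaction, arrhythmia and seizure are not impossible without ropivacaine; propofol allergy is itself an exclusion criterion in Section 6.3. On that reading the model will often fail, not always.

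Third, a reader might carry the 3% ceiling over to all complications and reject the GEE for the overall rate too. The ceiling applies to each listed ropivacaine event. It says nothing about complications of propofol or of the marrow procedure, which occur under both interventions. Even the three listed events together could reach 1 − 0.97³ = 8.7%, if each were at 3% and independent.

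Fourth, the logit link is stated for the primary outcome and only carried over here. This is a fair caution, but no other link is named.

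Fifth, a reader might infer from the safety-population sentence in Section 16.2 that A procedures leave the denominator. That depends on what study medication means there, which the section does not define, so it is not part of this point.

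Finally, the analyses are exploratory, and an exact paired test will seldom reach significance. Both are true. The first excuses low power, but not output unrelated to the evidence. The second is why the interval, and not the test, should carry the safety result.

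**Conclusion.** The point holds for specific adverse outcomes. If they are defined by relatedness, the between-drug odds ratio has no finite estimate at any sample size. If they are counted by type, the chance that one intervention has no events is 84%, 60% or 39% at 1%, 2% or 3%. Those percentages rest on assumed equal, independent rates and 50 completed procedures per intervention. The trial fits show that the stated method can return a confident but meaningless p-value without warning; they come from one software implementation and assume the primary outcome's logit link, so the exact printed values would differ elsewhere. The point does not reach the overall complication rate where both interventions have enough events. The correction is worth making before analysis, but it concerns an exploratory secondary analysis and leaves the primary conclusion and the sample size as they are.

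**What to change.** In Section 14.0, for specific adverse outcomes:

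- Define each event by type, regardless of attribution.
- Alongside the tabulation in Section 16.2, report counts per procedure by intervention actually received, with every study procedure in the denominator and Clopper-Pearson 95% intervals.
- Report events judged related to ropivacaine for Intervention B only, without a between-drug contrast.
- Make any between-intervention comparison by an exact paired method, such as exact McNemar, in place of GEE.
- Keep the GEE for the overall complication rate only when both interventions have enough events, with the minimum stated in advance; otherwise use the exact method.

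The cost is wording only, with no new data or patients. There would be no order-adjusted comparison for specific events, and the paired test leaves out patients with one procedure, who remain in the counts and intervals.
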